13.4 Health Insurance Portability and Accountability Act (HIPAA)

Study sites may be required by their institutions to obtain authorization from participants for use of protected health information. Sites will be responsible for communicating with their IRBs or Privacy Boards and obtaining the appropriate approvals or waivers to be in regulatory compliance.

13.5 Investigator Assurances

Each community treatment program site (CTP) must file (or have previously filed) a Federal Wide Assurance (FWA) with the DHHS Office for Human Research Protection setting forth the commitment of the organization to establish appropriate policies and procedures for the protection of human research subjects, with documentation sent to NIDA or its designee. Research covered by these regulations cannot proceed in any manner prior to NIDA receipt of certification that the research has been reviewed and approved by the IRB provided for in the assurance (45 CFR 46.103(b) and (f)). Prior to initiating the study, the principal investigator at each study site will sign a protocol signature page, providing assurances that the study will be performed according to the standards stipulated therein.

13.6 Financial Disclosure

All investigators will comply with the requirements of 42 CFR Part 50, Subpart F to ensure that the design, conduct, and reporting of the research will not be biased by any conflicting financial interest. Everyone with decision-making responsibilities regarding the protocol will have an up-to-date signed financial disclosure form on file with the sponsor.

13.7 Clinical monitoring

Investigators will host periodic visits by NIDA contract monitors who will ensure all study procedures are conducted and that study data are generated, documented and reported in compliance with the protocol, GCP, and applicable regulations. These monitors will audit, at mutually agreed upon times, regulatory documents, case report forms (CRFs), and corresponding source documents for each participant.

Qualified node personnel (Node QA monitors) will provide site management for each site during the trial. This will take place as specified by the local protocol team, node PI or lead team and will occur as often as needed to help prevent, detect, and correct problems at the study sites. Node staff will verify that study procedures are properly followed and that site staffs are trained and able to conduct the protocol appropriately. If the node staff's review of study documentation indicates that additional training of study personnel is needed, node staff will undertake or arrange for that training. Details of the contract, node QA and data monitoring are found in the study QA monitoring plan.

13.8 Study documentation

Study documentation includes all case report forms, data correction forms, workbooks, source documents, monitoring logs and appointment schedules, sponsor-investigator correspondence, and signed protocol and amendments, Ethics Review Committee or Institutional Review Committee correspondence and approved consent form and signed participant consent forms.

Source documents include all recordings of observations or notations of clinical activities and all reports and records necessary for the evaluation and reconstruction of the clinical research study. Whenever possible, the original recording of an observation should be retained as the source document; however, a photocopy is acceptable provided that it is a clear, legible, and exact duplication of the original document.

13.9 Safety Monitoring

13.9.1 Data and Safety Monitoring Board (DSMB)

An independent CTN DSMB will examine accumulating data to assure protection of participants' safety while the study's scientific goals are being met. The CTN DSMB is responsible for conducting periodic reviews of accumulating safety and efficacy data. It will determine whether there is support for continuation of the trial, or evidence that study procedures should be changed, or if the trial should be halted, for reasons relating to the safety of the study participants, the efficacy of the treatment under study, or inadequate trial performance (e.g., poor recruitment).

13.9.2 Protocol Violations Reporting and Management

A protocol deviation is any departure from procedures and requirements outlined in the protocol. Protocol departures may occur on two levels, deviation versus violation. The difference between a protocol deviation and violation has to do with the seriousness of the event and the corrective action required. A protocol deviation is considered an action (or inaction) that by itself is not likely to affect the scientific soundness of the investigation or seriously affect the safety, rights, or welfare of a study participant. Protocol violations are departures that may compromise the participant safety, participant rights, inclusion/exclusion criteria or study data and could be cause for corrective actions if not rectified or prevented from re-occurrence. Protocol violations will be monitored at each site for (1) significance, (2) frequency, and (3) impact on the study objectives, to ensure that site performance does not compromise the integrity of the trial. The decision about whether a departure from the protocol will be designated as a protocol deviation or a protocol violation will be made by the protocol's Lead Investigator in conjunction with the CCC. The consequences will be specified and participating sites should be informed.

All protocol violations will be recorded in the Electronic Data Capture (EDC) system via the Protocol Violations CRF. Additionally, each site is responsible for tracking and reporting to their IRB as required. Protocol deviations will be noted by participating sites and reported to their IRBs as required. The CCC and the Data and Statistics Center 2 and the Lead Investigator must be contacted immediately if an unqualified/ineligible participant is randomized into the study.

13.9.3 Confidentiality

By signing the protocol signature page the investigator affirms that information furnished to the investigator by NIDA will be maintained in confidence and such information will be divulged to the IRB, Ethical Review Committee, or similar expert committee; affiliated institution; and employees only under an appropriate understanding of confidentiality with such board or committee, affiliated institution and employees. The lead investigator will obtain a federal Certificate of Confidentiality (CoC), protecting participants against disclosure of sensitive information (e.g., drug use), and will distribute it to all sites when received. The NIH office that

issues the CoC will be advised of changes in the CoC application information. Participating CTP sites will be notified if CoC revision is necessary.

Participant records will be held confidential by the use of study codes for identifying participants on CRFs, secure storage of any documents that have participant identifiers, and secure computing procedures for entering and transferring electronic data.

13.9.4 Adverse Events (AEs)

The Lead Investigator (LI) may appoint a Study Clinician (MD, PhD, or PI) for this study, who will review or provide consultation for each Serious Adverse Event (SAE) as needed. These reviews will include an assessment of the possible relatedness of the event to the study intervention or other study procedures. The Study Clinician will also provide advice for decisions to exclude, refer, or withdraw participants as required. In addition, NIDA will assign a Medical Monitor and Safety Monitor to this protocol to independently review the safety data, present it to the DSMB for periodic review, and provide PIs a Safety Letter when necessary. The medical monitor will determine which safety events require expedited reporting to NIDA, the DSMB and regulatory authorities. This will include events that are serious, related and unexpected. The study staff will be trained to monitor for and report adverse events and Serious Adverse Events (SAEs).

Each of the CTPs has established practices for managing medical and psychiatric emergencies, and the study staff will continue to utilize these procedures. Treatment providers at each CTP will be responsible for monitoring participants for possible clinical deterioration or other problems, and for implementing appropriate courses of action.

Definitions of Adverse Event and Serious Adverse Event

Standard definitions for adverse events and serious adverse events, their identification, characterization regarding severity and relationship to therapy and processing are described in Appendix A.

Reportable Adverse Event and Serious Adverse Event

Adverse Events

For the purpose of this study, the following AEs will not require reporting in the data system but will be captured in the source documentation as medically indicated:

- Grade 1 (mild) unrelated event
- Grade 2 (moderate) unrelated event.

This would typically include physical events such as headache, cold, etc that was considered unrelated to study participation.

Serious Adverse Events

For the purpose of this study, the following SAEs will not be recorded in the data system but will be documented in the source documentation as medically indicated. They would be reported to local IRBs per local IRB guidelines:

- Admission to a hospital or freestanding residential facility for drug detoxification; the event will be captured on the NMS form (described above).
- Admission to a hospital/surgery center for preplanned/elective surgeries;
- Admission to a hospital for scheduled labor and delivery;
- Inpatient hospital admission for a medical event (i.e. gallbladder surgery, pneumonia)

14.0 STATISTICAL ANALYSES

14.1 Outline of Study Hypotheses

14.1.1 Two Co-Primary Hypotheses

- Due to the comprehensive, science-based, psychosocial treatment offered by TES, we hypothesize that the modified TAU+TES intervention will promote significantly greater drug and heavy alcohol use abstinence compared to the TAU arm during the 12 weeks of treatment. Specifically, we will use longitudinal, piecewise, logistic regression to model all 12 weeks, but test for a treatment difference only during the last 4 weeks of the treatment phase.
- We hypothesize that the modified TAU+TES intervention will promote significantly greater treatment retention relative to TAU during the 12-week treatment phase.

14.1.2 Secondary Hypotheses

- We hypothesize that differential outcomes in drug abstinence observed across groups during treatment will continue to be observed at the 3- and 6- month follow-up time points.
- We expect that psychosocial functioning will improve in the group that received the modified TAU+TES at 3- and 6-month follow-up time points relative to the TAU alone condition.
- We hypothesize that the modified TAU+TES intervention will be cost-effective relative to TAU from both the health care sector and CTP program perspectives at the 3- and 6-month follow-up time points.
- We hypothesize that individuals in modified TAU+TES will show significant increases in coping skills acquisition (as measured via the Coping Strategies Scale) relative to TAU at end of treatment and 3- and 6-month time points, and we expect that coping skills will be shown to serve as a mediator substance use outcomes.

14.2 Primary Outcome Measures

This study will include two co-primary outcome measures, a measure of abstinence from all drugs and heavy drinking days and a treatment retention measure, as described below. The primary endpoints will be analyzed according to the intent-to-treat principle. This means that patients will be analyzed according to the randomized treatment regardless of the subsequent sequence of events. In other words, patients will be considered to belong to the randomized group even though they may not be perfectly compliant or may not follow the prescribed treatment.

14.2.1 Primary Abstinence Measure

The first primary outcome measure will be an indicator of abstinence from all drugs of abuse and heavy drinking days in the interval between the two biweekly urine collections. We refer to this interval as a "half-week", since it will be 3-4 days on average. Thus the primary abstinence measure is actually a set (i.e. vector) of binary indicators over the 24 half-weeks comprising the 12 week treatment phase of the study. Evidence of abstinence from drugs of abuse in a given half-week will be obtained via urine toxicology measured at the end of the half-week and via self-reported use assessed by the TimeLine Follow-Back. Heavy drinking days will be assessed via the TimeLine Follow-Back. Thus, the primary outcome measure will be based on urineconfirmed self report of drug/alcohol use. Participants will be considered negative from all substances (abstinent) in a given half-week if their urinalysis at the end of the half-week and their self-report data both reflect the absence of drug and heavy alcohol use. If either a urine sample or self-report data indicate drug or alcohol use in a given half-week, the participant will be considered positive for substance use (non-abstinent) for that half-week. Table 1 gives the half-week outcome coding for all possible joint occurrences of urinalysis and self-report, including where either or both are missing. Note that self report for a particular half-week is missing only if one (or more) follow-back day is unobserved and all other days in the half-week are reported negative or all days in the half-week are missing. If the urine sample at the end of a given half-week is missing, and the subject reports no use, then they are considered to be missing the indicator of abstinence for that half-week.

Table 1. Half-week outcome coding corresponding to UDS and self-report outcomes.

		Urine Drug Screen			
		Positive	Negative	Missing	
	Positive ^a	+	+	+	
Self Report	Negative ^b	+	-	Missing	
	Missing ^c	+	Missing	Missing	

^a Positive self report indicates ≥1 reported non-abstinent day in the half-week.

^b Negative self report indicates all days in the half-week were reported abstinent.

^c Self report is missing if there is no TLFB data for ≥ 1 day in the half-week.

Missing urine sample collections require additional assumptions in order to define the intervals for each half-week. For example, if a subject contributed a urine sample only on day two of the week, then we must specify a rule for deciding when the second urine collection should have been made. Table 2 describes this rule set for setting a date of collection for a missing urine sample when there is one urine specimen obtained in a week. If there are no urine samples collected in a particular week, then the dates of collection are assumed to be days 3 and 6.

Table 2. Specifying collection dates for missing urine samples.

		Day in a Given Week					
Observed Collection Day	1	2	3	4	5	6	7
Imputed Collection Day	6	6	6	2	3	3	3

In this way, we can define half-weeks even if the urine screen defining the end of the interval was not collected. Missing data in the primary abstinence measure, as defined in Table 1, will be excluded from the primary analysis. However, secondary analyses of the primary abstinence measure will utilize other methods of handling missing data (see Section 14.13). In the event two urine screens were collected on consecutive days, only the first sample will be considered for the analysis of all abstinence outcomes.

See Sections 14.6 and 14.7 for descriptions of secondary analyses using alternative outcome measures of abstinence: the total number of abstinent weeks and the number of consecutive weeks abstinent.

14.2.2 Primary Retention Measure

The second primary outcome measure will be time to drop-out from treatment (including TAU) and will be treated as time-to-event data (time until last face to face contact). Drop-out is considered an event, and for each participant who does not complete all 12 weeks of treatment, time (in weeks) from start of treatment to drop-out from treatment is recorded, with values potentially ranging from 0 through 11. Participants completing all 12 weeks of treatment will have time value recorded as 12 weeks and will be considered censored at that time.

14.3 Rationale for Considered Magnitude of Treatment Effects

Effect sizes and variability estimates were obtained from data from prior CTN trials that had some similar design characteristics as the planned trial (CTN MIEDAR study protocols #006 and 007 published in Petry et al., 2005a). Specifically, these prior CTN trials evaluated a similar non-computerized, motivational incentives intervention for a similar duration (12 weeks) as will be evaluated in the present trial. As prior research by our group and others (e.g., Bickel, Marsch et al., 2008; Marsch et al., 2007b) has demonstrated the comparable efficacy of computerized and non-computerized psychosocial interventions, we expect the effect sizes to be observed in the planned trial will be comparable to those observed in this prior CTN trial (details of effect sizes discussed in Section 14.4. below).

14.4 Sample Size and Statistical Methods for Primary Outcomes

We propose to recruit a sample size of about 500 participants (about 250 per condition). We plan to collaborate with approximately 10 (range 8-12) CTP sites to recruit participants for this trial, and we plan for each collaborating CTP to recruit approximately 40-60 participants in one year (for a total of about 500 participants enrolled in year 1). As discussed below, these sample size calculations are based on having sufficient power to detect group differences in our primary outcome measures of (1) abstinence during the 24 half-weeks of treatment (calculated as urine confirmed self-report) and (2) treatment retention.

Hence, the overall null hypothesis of the study has two individual null hypotheses, each corresponding to one primary endpoint. The first individual null hypothesis H_{0-1} states that the TAU+TES therapy does not change abstinence as compared to the TAU arm of the trial. The second individual null hypothesis H_{0-2} states that the TAU+TES therapy does not change treatment retention as compared to TAU.

The alternative overall hypothesis states that the TAU+TES therapy changes at least one primary endpoint (abstinence or retention) as compared to TAU. It is expected that the TAU+TES therapy, when compared to TAU alone, will increase abstinence and improve retention in treatment.

Since the study considers simultaneously two co-primary endpoints, one needs to account for multiplicity of comparisons to protect type I error. During analysis we propose to use the method proposed by Hochberg (Hochberg, 1988). The method states that the overall null hypothesis can be rejected if either of the following two conditions holds:

- Both endpoints are significant at the $\alpha = 0.05$ significance level (i.e. both individual null hypotheses H_{0-1} and H_{0-2} are rejected at $\alpha = 0.05$)
- Either endpoint is significant at the $\alpha = 0.025$ significance level (i.e. at least one of the two individual null hypotheses H_{0-1} or H_{0-2} is rejected at $\alpha = 0.025$).

Sample size estimates for the Hochberg approach require simulations. Hence, the sample size computations below will be based on a more conservative (i.e. requiring somewhat larger sample size) Bonferroni adjustment approach, in which both individual hypotheses H_{0-1} and H_{0-2}

need to be rejected at the α =0.05/2 = 0.025 level. However, for analysis, as mentioned above, we will use the more powerful Hochberg approach.

14.4.1 Statistical Methods and Sample Size Considerations for Primary Abstinence Measure

Let y_{it} denote the indicator of abstinence for participant i (i=1,...,n) during half-week t (t=1,...,24). The vector of outcomes for a participant, $y_i = (y_{i1}, ..., y_{i24})$, constitutes the primary outcome measure of abstinence. The precise definition of half-week t is the time between the (t-1)th urine collection and the t^{th} urine collection. For example, consider a participant whose third and fourth urine collections fall on days 8 and 11 of the treatment phase of the study. The fourth half-week would then comprise TLFB self report data from days 8 through 10 confirmed by the urinalysis on day 11. To be considered abstinent in the fourth half-week ($y_{i4} = 1$), the participant must report no drug or heavy alcohol use on days 8, 9 and 10 and the urine sample collected on day 11 must be negative. If that urine sample is missing for any reason and no use was reported via TLFB, then the indicator of abstinence for the participant is missing for the fourth half-week. If on days 8-10 there is at least one self-reported day of heavy drinking or drug use (i.e., positive self report) or the urinalysis is positive, then the participant is considered not abstinent ($y_{i4} = 0$).

The primary outcome analysis of abstinence will evaluate whether assignment to TAU+TES is associated with more abstinence in the last four weeks of the treatment phase of the study compared with those assigned to TAU. Previous CTN studies have noted that after a certain period of time (approximately four weeks), the effect of both TAU and contingency management therapies stabilize. To minimize the possibility of a time by treatment interaction affecting the primary comparison between the two treatment groups, we will model all 24 half-weeks, but only test for a treatment difference during the last eight half-weeks of the 12-week treatment phase.

Since the primary outcome of abstinence is binary and measured over the 12 weeks of the treatment phase, a longitudinal logistic regression model will be the used for the analysis. The logistic model has two components: a linear association between treatment and the log-odds of abstinence over the first 16 half-weeks, and a constant treatment effect (odds ratio) beginning at half-week 17, and extending through the end of the treatment phase. Figure 1 gives a graphical representation of this "piecewise linear" model. The intercepts α_0 and α_1 are the log-odds of abstinence in the first half-week for the TAU and TAU+TES arms respectively. β_0 and β_1 are the increase in the log-odds of abstinence across consecutive half-weeks (for *t*=1,...,16). The slope of the log-odds line after half-week 16, that is common to both treatment arms, is captured by Φ .

Letting TES_i be an indicator of whether a participant was randomized to the TAU+TES arm, the piece-wise model for all i (i=1,...,n) and t (t=1,...,24) is given by

logit $P(y_{it} = 1) = \alpha_0 (1 - TES_i) + \alpha_1 TES_i + \beta_0 (1 - TES_i) [17 + I{t < 17}(t - 17)]$

+ $β_1$ TES_i [17+I{*t*<17}(*t*-17)] + Φ I{*t*≥17}(*t*-17)

where $I{\cdot}$ is the indicator function. More simply, the logit $P(y_{it} = 1)$ can be split as follows:

[figure not shown]
t <17:
$$\alpha_0$$
 (1- TES_i) + α_1 TES_i + β_0 (1- TES_i) (*t*) + β_1 TES_i (*t*)

[figure not shown]
$$t \ge 17$$
: $\alpha_0 (1 - \text{TES}_i) + \alpha_1 \text{TES}_i + 17 \beta_0 (1 - \text{TES}_i) + 17 \beta_1 \text{TES}_i + \Phi (t-17)$

Further, we adjust for the two stratification factors. Let z_i be an indicator of whether the participant's primary drug of use is a stimulant, and x_i an indicator of whether the participant's baseline urine screen was positive. In this case the longitudinal logistic regression becomes:

$$\begin{aligned} t <& 17: \quad \gamma \ z_i + \eta \ x_i + \alpha_0 \ (1 - \mathsf{TES}_i) + \alpha_1 \ \mathsf{TES}_i \ + \beta_0 \ (1 - \mathsf{TES}_i) \ (t) + \beta_1 \ \mathsf{TES}_i \ (t) \\ t \geq& 17: \quad \gamma \ z_i + \eta \ x_i + \alpha_0 \ (1 - \mathsf{TES}_i) + \alpha_1 \ \mathsf{TES}_i \ + 17 \ \beta_0 \ (1 - \mathsf{TES}_i) \ + 17 \ \beta_1 \ \mathsf{TES}_i + \Phi \ (t-17) \end{aligned}$$

In this model the log-OR of abstinence associated with using a stimulant is captured by γ , and the log-OR associated with testing positive at baseline is denoted by η .

To adjust for the correlation of half-week abstinence indicators within participants, we will utilize the robust variance estimator from generalized estimating equation (GEE) methodology (Liang & Zeger, 1986). For the 24 binary outcomes within a participant, we will assume an autoregressive lag-1 covariance matrix. This correlation is then used to compute a robust variance estimator. One advantage of using GEEs is that the correlation of participants within the same CTP can also be incorporated without additional distributional assumptions, such as required by a mixed effects model. Further, the GEE variance estimates are robust to the potential misspecification of the auto-regressive lag-1 covariance matrix. This methodology will be implemented using PROC GENMOD in SAS v9.2.

The test of treatment effect in the last four weeks of the active treatment phase can be captured by testing whether the following contrast is equal to zero:

$$C = (\alpha_1 + 17 \beta_1) - (\alpha_0 + 17 \beta_0)$$

For sample size calculations, we used data from CTN-0006 to get estimates of: α_0 , α_1 , and η . In that study, both treatment arms had similar rates of abstinence in the first week, so we set $\alpha_0 = \alpha_1 = \log(0.2/0.8) = -1.39$ since the observed probability of abstinence during the first week of treatment was 20%. The observed log-OR of having a positive UDS at baseline (η) was

estimated as 2.65 with a 95% confidence interval of 1.97 to 3.34. The power analyses for the current study considered these three values of η . To simulate the data we also used CTN-0006 to estimate the probability of a positive UDS at baseline (20%). From a questionnaire completed by CTPs involved in the current study, on average, 27.5% of substance use patients in the CTPs were primary users of stimulants. There are no available data to suggest an appropriate estimate of the OR associated with being a stimulant user, so we considered ORs of 0.5, 1.0 and 2.0. From analyses of CTN-0006, there is no need to simulate a slope for the log-odds curves after half-week 16 since the slope is zero (i.e. Φ =0). Various values of β_0 and β_1 were considered that yielded estimates of the treatment odds ratio of 1.3, 1.5 and 1.8.

These parameter estimates were used to generate 24 half-week outcomes for 500 subjects. The correlation between the half-weeks within a participant was generated via a Markov Chain using estimated transition probabilities from CTN-0006. These estimates yielded a correlation between consecutive half-weeks of 0.56. Intermittent missing data indicators were also generated using a Markov Chain with the transition probabilities from CTN-0006, where the consecutive half-week correlation between being missing is 0.4. This yielded an overall probability of being missing at any half-week of 50%, as seen in Petry et al. (2005).

Table 3 provides power estimates for 500 participants and the detectable odds ratio (e^C). Regardless of the effect sizes for the two stratification factors, a clinically meaningful OR of 1.5 can be detected with 500 subjects and over 80%. In addition, this analysis may be conservative as the amount of missing data is expected to be much less than CTN-0006 since the proposed study will employ aggressive participant tracking strategies.

Assumed OR for Each Stratification Variable [†]		Power for Specific OR Values Capturing Treatment Effect of TAU+TES		
Primary Use of a Stimulant	Positive Baseline UDS [‡]	OR = 1.3	OR = 1.5	OR = 1.8
0.5	7	43%	86%	99%
1.0	7	43%	88%	100%
2.0	7	44%	89%	100%
0.5	14	40%	84%	99%
1.0	14	41%	86%	99%
2.0	14	43%	87%	99%
0.5	28	37%	81%	99%
1.0	28	39%	84%	99%
2.0	28	41%	86%	99%

Table 3. Power analysis for 500 participants (250 participants per treatment arm).

¹ Stratification factors used in randomization.

[‡]OR values observed in CTN-0006 (Petry et al, 2005a).

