14.4.2 Sample Size Considerations and Statistical Methods for Primary Retention Measure

If a participant did not complete 12 weeks of treatment, time of drop-out from substance abuse treatment will be recorded. If a participant completes all 12 weeks of substance abuse treatment then time to drop-out will be considered as censored at 12 weeks. Data from the TAU+TES and TAU groups will be displayed with Kaplan-Meier curves estimating the probability of retention in the CTP until time t, over time. The TAU+TES and TAU groups will be compared with a Log-Rank test stratified by site.

Assuming 50% retention at 12 weeks in TAU+TES group and 35% retention at 12 weeks in the TAU group (hazard ratio HR = log(0.35)/log(0.50) = 1.515), there is 90% power to reject H_{0-2} : HR=1.0 with the total sample size of 500 when considering two-sided α =0.025. Power is based on an unstratified log-rank test. Sample size computations were performed with the Power And Precision 2.1 package.

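### Table 3 powers the abstinence test on scattered missing data only, which does not fit the 35%/50% retention assumed for the other co-primary; with that drop-out, power at OR 1.5 is about 73-75%, not 86%

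*Protocol*

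**What the plan says.** Section 14.4.1 bases power for the abstinence co-primary on a simulation: "Table 3. Power analysis for 500 participants (250 participants per treatment arm"). Outcomes follow a Markov chain with correlation 0.56 between consecutive half-weeks. Missing-data indicators come from a second chain, described as intermittent, with consecutive correlation 0.4: "This yielded an overall probability of being missing at any half-week of 50"%. For OR 1.5, Table 3 gives 81% to 89%, summarised as over 80% whatever the stratification effects. The text adds that "this analysis may be conservative as the amount of missing data is expected to be much less than CTN-0006".

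The treatment contrast is tested in half-weeks 17-24 only. Section 14.2.1 excludes half-weeks with a missing indicator from the primary analysis.

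Section 14.4.2 powers the other co-primary differently: "Assuming 50% retention at 12 weeks in TAU+TES group and 35% retention at 12 weeks in the TAU group". Section 14.2.2 dates drop-out at the last face-to-face contact.

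On the baseline drug screen, the model codes y = 1 as abstinent and x = 1 as screen-positive, and says "the log-OR associated with testing positive at baseline is denoted by" η. That parameter is then "estimated as 2.65 with a 95% confidence interval of 1.97 to 3.34".

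**The concern.** Both calculations describe the same 500 people. If half to two thirds of an arm has had its last contact by week 12, missing data late in treatment come mainly in unbroken blocks, more of them under TAU. Half-weeks within a person are strongly correlated, so losing whole people costs more information than losing the same number of scattered half-weeks. The tested window is where drop-out is greatest.

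Table 3 is the justification of 500 participants for abstinence. The interim check in section 14.5 also compares the error variance with its assumed value, so an assumption that is too favourable would carry into that decision.

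**Working it through.** **Inputs.** From 14.4 and 14.4.1: 250 per arm; alpha ("need to be rejected at the α =0.05/2 = 0.025 level"); first-week abstinence 20%; 20% screen-positive; 27.5% stimulant users; η = 2.65; outcome correlation 0.56; the missing-data chain above; zero slope after half-week 16. From 14.4.2: retention 35% and 50%.

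**Assumed because not stated.** Two-sidedness, given only for retention ("when considering two-sided α =0.025"). The TAU slope, expressed as late TAU abstinence of 20-40% in the covariate-reference group. Exponential drop-out. Site clustering was not modelled.

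**1. Reproduce the plan.** I fitted the piecewise logistic GEE (AR(1) working correlation, robust variance) to large simulated samples, scaled the standard error of C to 500, and took power = Φ(ln 1.5/SE − 2.241). With 30% late TAU abstinence the nine OR 1.5 powers are 81.9-88.8%, against 81-89% printed. OR 1.8 also matches; OR 1.3 comes out 3-6 points above the table. Retention: events = 250 × (0.65 + 0.50) = 287.5, giving 89.9% against 90% stated.

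**2. Compare the missing-data pictures in half-weeks 17-24.**

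| | Chain (14.4.1) | Drop-out (14.4.2) |
|---|---|---|
| Mean missing | 50% | TAU 59%, TES 45%; average 52% |
| No data in window | 4% | TAU 52%, TES 39% |

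- Chain: 50% missing with correlation 0.4 gives P(missing again) = 0.5 + 0.5 × 0.4 = 0.7, so P(all eight missing) = 0.5 × 0.7^7 = 0.041.
- Drop-out: half-week 17 ends at week 8.5, so 1 − 0.35^(8.5/12) = 0.52 and 1 − 0.50^(8.5/12) = 0.39.

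**3. Power with the drop-out pattern** (OR 1.5, alpha 0.025).

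- Middle row (stimulant OR 1.0, baseline OR 14), 30% late TAU abstinence, drop-out only: 86% becomes 73%. A separately coded simulation gave 85% and 75%.
- The implied SEs are 0.4055/(2.241 + 1.080) = 0.122 and 0.4055/(2.241 + 0.619) = 0.142. The variance ratio is (0.142/0.122)² ≈ 1.35, so 500 participants carry the information of about 370.
- All nine rows: 68-77%. With 20% late TAU abstinence: 60-73%. With 40%: 72-78%.
- Drop-out plus intermittent gaps bringing overall missingness to 50%: 68% in the middle row.
- No missing data at all: about 93-97%.

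Drop-out alone leaves only 34% of all 24 half-weeks missing, below the 50% simulated, yet power is lower. A smaller amount of missing data does not by itself make Table 3 conservative.

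**4. Baseline-screen effect.** exp(2.65) = 14.2. With odds 0.25 for screen-negatives, screen-positives have odds 0.25 × 14.2 = 3.54, or 78% abstinent. The implied overall first-week rate is 0.8 × 0.20 + 0.2 × 0.78 = 0.316, not the observed 20%. Reversing the sign alone moves the middle row from 86% to 83% (81% to 74% at 20% late TAU abstinence; 88% to 87% at 40%). With the intercept re-centred, the negative sign gives more power than the positive one (86% against 78% at 30% marginal late TAU abstinence).

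**The case against.** **Table 3 is not a miscalculation.** It follows closely from its stated inputs, and a reader should not infer an arithmetic error in the OR 1.5 column. Nor is the 50% level contradicted: the drop-out average in the tested window is 52%. Both points stand. The conflict is one of pattern and arm difference.

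**Leaving treatment is not leaving the study.** Section 9.4.3 keeps people active for 12 weeks and still asks discharged participants for assessments. Section 9.5 allows off-site assessment, and 9.7 pays for urines in both arms. Total loss after last contact is thus a worst case. But 14.4.1 quantifies no recovery, and under Table 1 of 14.2.1 a half-week without urine can be scored only positive or missing, never abstinent. Recovery by self-report alone would not restore the simulated data.

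**The planned analysis is Hochberg, not Bonferroni.** Retention with 90% power at 0.025 has about 94% at 0.05 (1.282 + 2.241 − 1.960 = 1.563), so abstinence would usually be tested at 0.05. There, 73% becomes at most about 82% (0.619 + 2.241 − 1.960 = 0.900) and 75% about 83%. This recovers much of the loss in the middle row. The low end stays short: 60% becomes about 70% (0.253 + 0.281 = 0.534). Table 3 itself is stated on the Bonferroni basis.

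**Safeguards exist.** Section 14.5 plans a variance check with possible sample-size adjustment, and 14.13 plans missing-data sensitivity analyses. The first needs a sound benchmark; the second does not bear on power.

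**Conclusion.** The concern holds for the missingness pattern. Under the protocol's own 35%/50% retention, with no usable half-weeks after last contact, power at OR 1.5 and two-sided alpha 0.025 is about 73-75% in the middle row and roughly 60-78% over the strata settings and TAU slopes tried. It is lower still with added gaps. The over-80% statement and the remark on conservatism do not follow. The size rests on exponential drop-out, no recovery and an assumed TAU slope.

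A reader might infer that the trial is underpowered or that 500 is too few. The documents do not support that: recovery after drop-out is unknown, and Hochberg testing restores part of the loss.

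The sign of η contradicts the coding, and the overall 20% is used as the screen-negative intercept. A reader might take the sign as a cause of lost power. Alone it costs about 1-7 points and, re-centred, it gains some. It may be only a label, for instance an OR of later positive tests; the protocol does not show which was simulated. It is a secondary correction. Overall this should be fixed, but it does not threaten the design.

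**What to change.** - Re-run Table 3 with arm-specific monotone drop-out matching 35% and 50% retention, plus intermittent gaps, and state what recovery after drop-out is assumed.
- State the TAU slope (β0) used.
- Correct the sign of η or relabel it, and set the intercept so that overall first-week abstinence is 20%.
- Replace the over-80% and conservatism sentences with the resulting power or detectable OR, optionally also under Hochberg.
- Use the corrected variance as the benchmark for the interim check in section 14.5.

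The cost is one simulation re-run and a less favourable stated power. No change in sample size follows from this point.
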